#### Body weight

We will provide participants with a bathroom scale. Participants will be asked to place the scale on a level, hard surface (e.g., tile, wood), and weigh themselves in the morning shortly after waking with minimal clothing. Weekly body weight will be recorded in the myCircadianClock app.

#### Exit interview

After completion of the study (or earlier if a participant withdraws early from the study), a member of the study team will conduct an exit interview to understand the participants' experience being in the study. We will ask them what they liked about the study, did not like about it, what features they liked/did not like about the myCircadianClock app, if they would recommend the study to others, etc. This interview will be audio-recorded with explicit permission at the time of the interview, then transcribed for mixed methods data analysis.

**2** \* Describe all procedures already being performed for diagnostic or treatment purposes (if not applicable to the study, enter "N/A"):

N/A

**3** \* Describe the duration of an individual participant's participation in the study:

Participants will participate in the study for approximately 14 weeks, including consent, baseline assessments, a 12-week intervention, and an exit interview.

**4** \* Describe the amount of time it will take to complete the entire study:

Upon opening of the study, we expect that approximately 3-5 participants will be recruited per month for approximately 9 months. Data originating from questionnaires, actigraphs, glucose monitors, and exit interviews will be entered, processed, and/or cleaned (as applicable) as they come in. We will perform an interim analysis of feasibility of the study after the 10th participant is enrolled and make any logistical adjustments to the protocol as necessary. Data analysis will take place soon after all data are collected.

These data will be used to inform a follow-on randomized clinical trial, for example a phase II or multisite clinical trial. It is anticipated that at least two manuscripts will emerge from this study, the first of which will be submitted for publication within one year of the study closing (the primary aims paper).

**5** \* Describe any additional participant requirements:

None

ID: VIEW4E0280585B400  
Name: v2\_Study Procedures

## Sample Size and Data Analysis

If you uploaded a separate research protocol document in the 'Research Protocol' page, cite the applicable section and page numbers from that document in the answer boxes below.

1 \* Provide the rationale and sample size calculations for the proposed target population:

This is a two-arm pilot randomized controlled trial that will assess the feasibility of recruitment and retention to a 12-week TRE trial facilitated by the myCircadianClock app as well as the preliminary efficacy of TRE vs. a control arm on the treatment of cancer-related fatigue.

It is common that single-arm pilot studies implementing dietary interventions recruit 10-40 participants (e.g., TRE study among overweight older adults, n=10; ketogenic diet among patients with recurrent glioblastoma, n=20; lifestyle intervention including diet among overweight breast cancer survivors, n=14). In total, 30 participants will be recruited, and approximately 10-20% attrition is anticipated, providing evaluable data from approximately 25 participants. We had more dropouts than anticipated and are upping our sample size to 50 participants so that we can have about 25 participants with evaluable data.

2 \* Provide the plan for data analysis. Include in the description the types of comparisons that are planned (e.g., comparison of means, comparison of proportions, regressions, analysis of variance, etc.), which is the primary comparison/analysis, and how the analyses proposed will relate to the primary purposes of the study:

We will conduct an interim analysis of feasibility after 10 participants have been enrolled. If any unanticipated barriers arise in regard to feasibility of recruitment, data collection, and/or retention, logistical changes will be made to the protocol as appropriate.

Aim 1 assesses the feasibility of time-restricted eating over 12 weeks. We will note how many people we can screen; how many we can approach; how many are eligible; how many consent; and what percentage provide evaluable data at baseline and 12 weeks. Using data from myCircadianClock, we will extract how many days the participants ate within a 10-h window and the average length of the eating window at baseline, week 6, and week 12. We will consider a participant "adherent" if they ate within the 10-h window at least 80% of days. This goal is based on prior TRE studies. In regard to retention, it is hypothesized that at least 80% (24 out of 30) of those who provide baseline data also provide data at 12 weeks; this goal is based on colleagues' prior behavioral intervention studies with supportive care outcomes.

Aim 2 aims to provide estimates of efficacy comparing time-restricted eating vs. control on fatigue. Linear mixed models (LMMs) for longitudinal data will be used to assess the intervention effect on continuous outcomes (e.g., fatigue) accounting for correlations between the repeated measures. Generalized Linear Mixed Model (GLMM) analyses will be conducted to assess the effect of the intervention on count outcomes. The fixed effects included in the models will be treatment group (TRE versus control), time (baseline, 6 and 12 weeks), group-by-time interaction term and relevant covariates. Random effects will include individual patients. The hypotheses will be tested by evaluating the interaction term of group and time (i.e., 12 weeks). The results of the analyses together with the mean and SD of FACIT-F values as well as change scores will be used in planning future RCTs. All hypothesis testing will be at the two-sided level of 0.05. Following the intent-to-treat principle, all participants will be analyzed as randomized, regardless of their adherence with the intervention.

Mechanistic exploratory aims will be evaluated using the same analytical approach as for the primary aim. For circadian rhythm, we will use actigraphy and patient-reported myCircadianClock app data to measure objective symptoms of sleep quality. We can use the actigraph to assess activity in three axes, recorded as "counts." Counts are used to calculate the strength of circadian rhythms as well as deduce active periods and sleep measures (i.e., sleep latency, sleep efficiency, sleep duration, wake after sleep onset, daytime napping). To evaluate circadian activity, we will use a two-oscillator (12 and 24 hours) cosinor model to estimate key circadian rhythm parameters. Also at baseline and week 12, we will assess interstitial glucose concentrations using a continuous glucose monitor. From these data we will extract fasting glucose, average daily glucose, average waking and nocturnal glucose, maximum glucose, and area under the curve. We will explore associations between objective and subjective measures at baseline, adjusting for confounding factors (e.g., age, depression), in addition to changes over time and effects of the intervention on these parameters.

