## Justification, Objective, & Research Design

If you uploaded a separate research protocol document in the 'Research Protocol' page, cite the applicable section and page numbers from that document in the answer boxes below.

1 \* Describe the purpose, specific aims, or objectives of this research. State the hypothesis to be tested:

This pilot randomized controlled trial will test the effects of time-restricted eating vs. an unrestricted eating pattern (i.e., control) on persistent cancer-related fatigue, circadian rhythm, and metabolism. These data build upon a study conducted by [name] (PI) that established the feasibility and safety of time-restricted eating among cancer survivors—cancer survivors were willing and able to eat within a 10-hour window for 14 days. The specific aims are as follows:

Aim 1: To assess the feasibility of time-restricted eating for 12 weeks, utilization of the myCircadianClock app, continuous interstitial glucose monitoring, and the wrist-worn actigraph. We hypothesize that 80% of participants will provide evaluable data regarding their eating window via the app at baseline and 12 weeks. We also hypothesize that at least 80% of participants who are in the time-restricted eating arm and provide evaluable data will eat within a daily average window that is  $\leq 10$  hours.

Aim 2: To estimate the preliminary efficacy of a 12-week time-restricted eating intervention vs. an unrestricted eating pattern on patient-reported fatigue among fatigued cancer survivors, as measured using the Functional Assessment of Chronic Illness Therapy-Fatigue (FACT-F) questionnaire. We hypothesize that FACT-F fatigue subscale scores will be lower for those in the time-restricted eating group compared to the control group at week 12, controlling for baseline levels.

Mechanistic (exploratory) aims: To assess the effects of a 12-week time-restricted eating intervention vs. an unrestricted eating pattern on circadian rhythm (mesor, amplitude, and acrophase from actigraphy), sleep parameters (e.g., sleep efficiency), and biomarkers of metabolism (fasting blood glucose, glucose excursions).

1. To assess cross-sectional associations between circadian rhythms, metabolism, and fatigue at baseline.
2. To explore associations between changes in circadian rhythms, metabolism, and fatigue from baseline to 6 weeks and baseline to 12 weeks.
3. To explore associations between adherence to the intervention and changes in the same measures.

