## Study Procedures

**If you uploaded a separate research protocol document in the 'Research Protocol' page, cite the applicable section and page numbers from that document in the answer boxes below. (If this study is a collaborative UM/VA study please list each procedure that is being conducted and the locations where it is being conducted.)**

1 \* Describe all procedures being performed for research purposes only (these procedures would not be done if individuals were not in the study) and when they are performed, including procedures being performed to monitor subjects for safety or to minimize risks:

This is a pilot randomized controlled trial that works within the framework of the Obesity-Related Behavioral Intervention Trials (ORBIT) model for behavioral treatment development. This trial will assess the feasibility of our methods to conduct a 12-week randomized controlled trial that implements TRE as well as the preliminary efficacy of TRE vs. a control group on cancer-related fatigue. We will recruit 50 patients who are 2 months-2 years post-treatment for cancer (e.g., surgery, radiation, chemotherapy) and are suffering from moderate-severe cancer-related fatigue. They will be randomized 1:1 intervention:control (approximately 15 in each arm). This will be an open label study because, due to the nature of the intervention, it is not possible to blind participants and, due to the active involvement of the PI in data acquisition, it is not feasible to blind the PI. Participants will be told that we are using a new smartphone app that helps us explore how behaviors such as diet, exercise, and sleep are related to fatigue; some people will be asked to also engage in TRE while some will be asked to follow their normal eating patterns.

Participants will be recruited from the University of Maryland Medical System, including the Greenebaum Comprehensive Cancer Center, St. Joseph Medical Center, Upper Chesapeake Medical Center, and Baltimore Washington Medical Center. The whole study can be conducted remotely, but if the participant would prefer an in-person visit for consenting or any other study activity, we will meet them at either Greenebaum Cancer Center or the School of Nursing.

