## Participant Selection

1 \* How many local potential participants (or specimens/charts) do you anticipate will be screened for this study? **Screening includes determining potential participants' initial eligibility for and/or interest in a study.**  
300

2 \* How many participants (or specimens, or charts) will be enrolled/used for this study? **A local prospective participant is considered enrolled in the study when a UM-approved Informed Consent Document (not including separate screening consent forms) is signed.**

Local - the number being enrolled at this site:

50

Worldwide - the number being enrolled total at all sites (including local enrollment):

50

3 \* Gender:

Male  
 Female

4 \* Age(s):

0 to 27 days (newborn infants)  
 28 days to 12 months (Infant)  
 13 months to 23 months (Toddler)  
 2 to 5 years (Preschool)  
 6 to 11 years (Child)  
 12 to 17 (Adolescents)  
 18 to 88 years (Adult)  
 89 years and older

5 \* Race/Ethnicity:

All Races Included  
 American Indian or Alaskan Native  
 Asian/Other Asian  
 Asian/Vietnamese  
 Black or African American  
 Hispanic or Latino  
 Mixed Race or Ethnicity  
 Native Hawaiian or Pacific Islander  
 White or Caucasian

6

\* Language(s):

English  
 Chinese  
 French  
 Italian  
 Japanese  
 Korean  
 Local Dialect  
 Spanish  
 Vietnamese  
 Other

6.1 Specify Other:

7

\* Are you excluding a specific population, sub-group, or class?

Yes  No

7.1

If Yes, indicate your justification for excluding a specific population, sub-group, class, etc.:

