**2 \* Describe procedures for orderly termination:**  
Upon completion of data collection and return of the actigraph, each participant will be thanked for their participation in the study and compensated for their time.

If a participant withdraws (or is withdrawn) before the end of the study, they will be paid for the time they spent providing data and the study team will not contact the person anymore. A 10-20% withdraw rate is built into the study design and recruitment goal, so there should not be a need to replace participants who withdraw before completing the study.

**3 \* Describe procedures that will be followed when subjects withdraw from the research, including partial withdrawal from procedures with continued data collection:**  
If a participant wishes to withdraw from the study, we will ask if the participant would like to continue participation in some but not all of the research activities. If they would like to participate in only some of the research activities, we will note which ones and the participant will not be formally withdrawn from the study. If they wish to withdraw completely, a written withdrawal request is required and should be sent to the PI (email preferred). The written request for withdrawal will be included in the participant's study record as documentation of the reason for removing a participant from the study. If a participant makes a verbal request and does not provide a written request, the verbal request will be documented by the study team member who receives the request and added to the participant's study record. Data that have been collected thus far will be analyzed.

ID: VIEW4E1B5251F800  
Name: v2\_Withdrawal of Participants

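### Enrolment was raised from 30 to 50 for about 25 evaluable participants, but the arm size, the retention count and the withdrawal allowance still match the 30-participant plan

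*Combined protocol and SAP*

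**What the plan says.** All of the following is current text in the combined protocol and SAP.

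- **Sample Size and Data Analysis, item 1**, first sets out a plan: "In total, 30 participants will be recruited, and approximately 10-20% attrition is anticipated", giving evaluable data from about 25. It then reports more dropouts than expected and says the investigators "are upping our sample size to 50 participants so that we can have about 25 participants with evaluable data".
- **Study Procedures, item 1**, adopts the new total: "We will recruit 50 patients who are 2 months-2 years post-treatment for cancer". **Participant Selection, item 2**, also gives 50.
- The next sentence but one in Study Procedures begins from those patients: "They will be randomized 1:1 intervention:control (approximately 15 in each arm").
- **Sample Size and Data Analysis, item 2 (Aim 1)**, sets the retention target: "it is hypothesized that at least 80% (24 out of 30) of those who provide baseline data also provide data at 12 weeks".
- **Withdrawal of Participants, item 2**, states: "A 10-20% withdraw rate is built into the study design and recruitment goal". It concludes that people who withdraw should not need replacing.

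Two timing rules matter. Participant Selection fixes enrolment at consent: "A local prospective participant is considered enrolled in the study when a UM-approved Informed Consent Document" is signed. Study Procedures places randomisation after the baseline week.

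**The concern.** The total was changed, but three figures that depend on it still agree with 30 and not with 50. They are a planned arm size, a feasibility threshold and an attrition allowance.

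The retention figure matters most. Retention is part of Aim 1, and the results are meant to inform a follow-on trial. The target is now given as a percentage of people who provide baseline data and also as a count tied to 30. If some number other than 30 provide baseline data, the percentage and the count can give opposite answers on the same data.

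The withdrawal allowance matters for a similar reason. Anyone planning the next trial from that section would use 10-20%, a rate that the current sample size does not use.

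**Working it through.** **Inputs.** From Sample Size and Data Analysis: 30 recruited, 10-20% attrition, about 25 evaluable; then 50 for about 25 evaluable; retention of 80%, written as 24 of 30. From Study Procedures: 1:1 allocation, about 15 per arm. From Withdrawal of Participants: 10-20%.

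**1. The 30-participant plan reproduces.** Evaluable = N × (1 − loss).
- 30 × 0.90 = 27; 30 × 0.85 = 25.5; 30 × 0.80 = 24. All are close to 25.
- 30 / 2 = 15 per arm, and 0.80 × 30 = 24. Both match the text exactly.

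**2. The 50-participant plan.** Implied loss = 1 − evaluable / N.
- 1 − 25/50 = 50%. If about 25 is taken to mean 23 to 27, the loss is 46% to 54% (1 − 27/50 and 1 − 23/50).
- For comparison, 30 to 25 is 1 − 25/30 = 16.7%.

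**3. The 10-20% allowance against 50.**
- 50 × 0.90 = 45 and 50 × 0.80 = 40, so 40-45 evaluable, not 25.
- Working back, 25/0.90 = 27.8 and 25/0.80 = 31.25, so 28 to 32 enrolled would be enough.

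**4. Arm size.** 50/2 = 25 if everyone enrolled is randomised, so 25 is the maximum. The stated 15 corresponds to 2 × 15 = 30 randomised.

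**5. Retention.** The documents do not say how many people will provide baseline data, so three values are shown. Evaluable participants are taken to be those with week-12 data.

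| Provide baseline data | 80% of them | 24 as a share | 25 as a share | 23 to 27 as a share |
|---|---|---|---|---|
| 30 | 24 | 80% | 83.3% | 76.7% to 90% |
| 40 | 32 | 60% | 62.5% | 57.5% to 67.5% |
| 50 | 40 | 48% | 50% | 46% to 54% |

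Because 25/0.80 = 31.25, 25 completers meet the 80% target only if no more than 31 people provide baseline data. The count of 24 is reached in every row.

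**The case against.** The strongest defence is that the figures may refer to different stages. Enrolment is counted at consent, randomisation comes after the baseline week, and the retention denominator is people with baseline data. If about 20 of the 50 were lost between consent and randomisation, about 30 would be randomised. Then 15 per arm is right, 24 of 30 is right, and 25 of 30 (83%) meets the target. Loss after randomisation would be 5/30 = 16.7%, which lies within 10-20%.

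This reading is possible, so it is not established that the arm size and the 24 of 30 are leftovers. But the documents state no such loss, and in Study Procedures the people being randomised are most naturally the 50 just mentioned. Nor does the reading rescue the withdrawal section, which says its rate is built into the recruitment goal. That goal is now 50 for about 25.

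Three further objections have force:

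- The wording of the retention target puts the percentage first and the count in parentheses. Nothing says that retention will be judged as 24 completers whatever the denominator. The count is a source of ambiguity, not a declared pass rule.
- A reader might infer that the withdrawal rate is now 50%. The documents do not support that. The 50% is inferred from 25/50 and is a share not evaluable. Withdrawal of Participants, item 3, keeps people who continue only some activities from being formally withdrawn, so the two quantities differ.
- A reader might infer that the other Aim 1 hypothesis, "We hypothesize that 80% of participants will provide evaluable data regarding their eating window via the app at baseline and 12 weeks", is already contradicted by 25 of 50. That follows only if its denominator is everyone enrolled, which the documents do not say.

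Finally, this is a pilot without a power calculation, and participants are analysed as randomised. No test or estimate changes.

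**Conclusion.** The point holds as an inconsistency between current figures. The sample size section implies about 50% of enrolled participants not evaluable (46% to 54% if about 25 means 23 to 27), whereas the withdrawal section builds 10-20% into the recruitment goal. That conflict remains on either reading of where the losses occur.

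For the arm size (15 stated, at most 25 implied) and the 24 of 30, the conclusion is conditional. They match the 30-participant plan exactly and could stand under the 50-participant plan only with an unstated loss of about 20 people before randomisation. With 40 or 50 baseline providers, 25 completers would be 62.5% or 50%, short of 80%, while still exceeding 24. Those two denominators are illustrations; the true number is not given.

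The matter is worth correcting because a feasibility threshold and a planning assumption are affected. It does not undermine the efficacy analysis.

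**What to change.** 1. **Study Procedures, item 1:** restate the expected number randomised per arm. It is at most about 25, and the sponsor should supply the figure.
2. **Sample Size and Data Analysis, item 2:** delete the 24-out-of-30 count and keep the pre-specified 80% of all who provide baseline data.
3. **Withdrawal of Participants, item 2:** replace the 10-20% allowance with the loss the sponsor now assumes, given separately before and after randomisation and consistent with 50 enrolled for about 25 evaluable.

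The correction should not write in 50% as the withdrawal rate, and it need not impose a denominator on the evaluable-data hypothesis in Aim 1.

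The cost is a wording change submitted as a modification, with no additional participants or data. The downside is that the stated feasibility assumptions will look less favourable.

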Potential participants will be identified using four methods: (i) screening medical records, (ii) direct referral from providers (e.g., nurses, nurse navigators, physicians), (iii) flyers, and (iv) advertising via standard UMB- and ICTR-networks. The study staff will screen for potential participants using EPIC or, alternatively, patients may be referred to the study team by a provider or acquaintance. Initial contact will occur via the following methods: i) the treating oncologist or a member of the medical team (e.g., nurse practitioner) will introduce the study to the participant via a clinic appointment (in person or telehealth) and inquire if it would be okay for our study team to talk with them after their visit or contact them, ii) with approval of the treating oncologist or a designee, a recruitment letter will be sent to the potential participant briefly describing the study and asking them to contact us if they would like more information, and iii) with approval of the treating oncologist or a designee, a message will be sent to the potential participant via MyPortfolio briefly describing the study and asking them to contact us if they would like more information. If a potential participant is interested, the study team will provide more information about the study in-person or via phone.

The study activities are briefly described here; the study schema is illustrated in Figure 1 (see Additional Documents, "schema-data-collection.pdf," page 1).

At baseline, participants will complete an on-study form that includes demographics and clinical characteristics as well as questionnaires (see below). We will obtain a baseline body weight measurement. For one week (week 0), participants will wear an actigraph (i.e., activity tracker) and a continuous glucose monitor and complete a food log using the myCircadianClock app.

After the baseline period, they will be randomized 1:1, TRE:control. Those in the time-restricted eating group will be asked to eat all food and beverages in a self-selected 10-hour window during the day. The start time of the window can be chosen based on the participant's schedule and preferences, but it should be the same for the duration of the study. We will not restrict what people eat. Black coffee and unsweetened tea will be allowed before the window, and water and medications are allowable any time. Those in the control group will be asked to not make any changes to their current dietary patterns.

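### Aim 1 carries two unreconciled 80% data-provision targets, on different numerators and denominators, and the plan does not say which one decides feasibility

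*Combined protocol and SAP*

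**What the plan says.** Justification, Objective, & Research Design (item 1, Aim 1) states: "We hypothesize that 80% of participants will provide evaluable data regarding their eating window via the app at baseline and 12 weeks". Participants is not defined there.

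Sample Size and Data Analysis (item 2, Aim 1) does two things. It lists counts to be noted, including the number consenting and "what percentage provide evaluable data at baseline and 12 weeks", with no threshold and no stated denominator. Then, under retention, it hypothesises that "at least 80% (24 out of 30) of those who provide baseline data also provide data at 12 weeks". That is the only 80% threshold for data provision in the analysis plan. It does not say what kind of week-12 data is meant.

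Item 1 of the same section shows where the 30 comes from: "In total, 30 participants will be recruited, and approximately 10-20% attrition is anticipated". It goes on to say that dropout was higher than expected and that the team is "upping our sample size to 50 participants so that we can have about 25 participants with evaluable data". Participant Selection also gives 50.

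Two further places bear on the denominators. Participant Selection says: "A local prospective participant is considered enrolled in the study when a UM-approved Informed Consent Document" is signed. Study Procedures describes week 0 (food log, actigraph, glucose monitor, questionnaires) and then says: "After the baseline period, they will be randomized 1:1, TRE:control".

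**The concern.** A person who consents and leaves before giving any baseline data fails the target in the aims, if participants means everyone enrolled. In the analysis plan the same person is not counted at all. The numerators differ too: evaluable eating-window data from the app at two time points in one, unspecified data at week 12 in the other.

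Feasibility is the first aim of this pilot, and Study Procedures says that the data will inform a follow-on trial. If neither target is named as the deciding one, the choice can be made after the counts are known, and the same results can be described as meeting or missing the 80% mark.

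**Working it through.** **The plan's own figure.** 0.80 × 30 = 24, so 24 out of 30 reproduces. The 30 is the original recruitment number: 10-20% attrition from 30 leaves 27 to 24, matching the roughly 25 evaluable that item 1 of the sample-size section expects. The bracket therefore counts recruits, while the words beside it describe people who gave baseline data. The two agree only if nobody is lost before giving baseline data.

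**Restated for the current N.** 0.80 × 50 = 40 of 50.

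**Where the two targets part.** Let N be the number enrolled, b the number giving baseline data and c the number with qualifying week-12 data. To isolate the denominator, use the same c for both. The aims version is met if c ≥ 0.8N; the analysis-plan version is met if c ≥ 0.8b. They disagree when 0.8b ≤ c < 0.8N. N is from the documents; b and c are assumed, because the documents do not split losses into before and after baseline.

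| N | b (assumed) | c (assumed) | c/b | c/N | Values of c that disagree |
|---|---|---|---|---|---|
| 50 | 50 | 40 | 80% | 80% | none |
| 50 | 48 | 39 | 81.3% | 78% | 39 |
| 50 | 45 | 36 | 80% | 72% | 36 to 39 |
| 50 | 40 | 32 | 80% | 64% | 32 to 39 |
| 50 | 31 | 25 | 80.6% | 50% | 25 to 31 |
| 30 | 28 | 23 | 82.1% | 76.7% | 23 |

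Two early losses are the fewest that can produce a disagreement at either N. With one loss, both versions need the same count: 0.8 × 49 = 39.2, so 40; 0.8 × 29 = 23.2, so 24.

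**The plan's expected 25 of 50.** On all enrolled this is 25/50 = 50%. On baseline providers it is 25/40 = 62.5%, 25/35 = 71.4%, 25/32 = 78.1% or 25/31 = 80.6%. For this particular count the two versions disagree only if 31 or fewer gave baseline data, that is, if at least 50 − 31 = 19 were lost first.

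**Chance of meeting each version.** Assume N = 50, b = 45 and independent 85% retention after baseline. Then P(c ≥ 36) = 0.87 for the analysis-plan version and P(c ≥ 40) = 0.31 for the aims version. With b = 50 both are 0.88.

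**The case against.** The strongest reply is that these are two separate measures. The aims sentence concerns completeness of app data and does not mention retention. The analysis plan introduces its 80% as a retention goal with its own basis, colleagues' earlier behavioural trials. Different measures may properly have different denominators, and retention after baseline is a sensible planning figure when randomisation comes after the baseline week. This stands as far as it goes. But on that reading the 80% hypothesis in the aims has no stated test in the analysis plan, so a correction is still needed.

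A reader might infer that the conditional target conceals run-in loss. The documents do not support that. The analysis plan will report how many consent and what percentage give evaluable data, and the Waiver/Alteration of Authorization section plans a published CONSORT diagram.

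A reader might also infer that the trial already expects to fail Aim 1 at 50% and that the conditional wording rescues it. That goes too far. The 25 is a sample-size planning figure, evaluable is not defined there, and a rescue needs at least 19 losses before baseline data, a split given nowhere.

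It is also fair to say that 24 out of 30 is compatible with planning for every recruit to give baseline data, and that all enrolled is an inference from the form's definition of enrolment. If participants meant those randomised, the gap would shrink to randomised people without baseline data. Finally, no stop-or-go rule hangs on this 80%: the only modification criterion in the monitoring plan concerns accrual.

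**Conclusion.** The point holds as an unreconciled feasibility threshold. Two 80% targets stand under Aim 1 with different numerators and denominators, the plan does not say which decides the aim, and the count beside one of them is out of date for 50 participants.

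The two can give opposite answers from two early losses upward. At an assumed 45 of 50 with baseline data, any completer count from 36 to 39 meets one and misses the other. This rests on reading participants as all enrolled, on using the same week-12 count for both versions, and on an assumed number of early losses. It does not show that early loss is hidden or that the target will be missed. It should be corrected because it settles what a met Aim 1 means, but it does not affect the efficacy analysis.

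**What to change.** In the Aim 1 paragraph of Sample Size and Data Analysis:

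- Name the hypothesis from the aims as the deciding test. Numerator: participants with evaluable app eating-window data at both baseline and week 12. Denominator: all enrolled, as Participant Selection defines enrolment. Threshold: 80%, that is, 40 of 50.
- Replace 24 out of 30, and say what makes app data evaluable.
- Keep retention to week 12 as a named secondary rate, by arm, and state whether it starts from baseline data or from randomisation.
- Report run-in completion, enrolled to randomised, beside it.

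The cost is wording only. Consent and evaluable-data counts are already planned, and the remaining counts are those a CONSORT diagram needs. No procedure or participant burden changes. The downside is that the headline feasibility rate may look less favourable than one conditional on baseline data.
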